11.3. Accrual, Follow-up, and Sample Size

We will randomize 110 AGYW in a 1:1 ratio to either our adapted intervention or standard-of-care mental health services over a 12-month study period (approximately 9-10 AGYW enrolled per month). Based on current levels of AGYW receiving PrEP at the public health clinic in Johannesburg, and reporting symptoms of common mental disorders and receiving referral services, we will likely need to screen approximately 18-20 AGYW per month to meet our enrollment targets. Based on prior PrEP studies with AGYW in this setting (HPTN 082, PrEP SMART, POWER), we expect to retain 85-90% of AGYW through three months of follow-up.

For our primary outcome of PrEP adherence, if we assume 40% PrEP adherence in the standard-ofcare arm (as was seen in the HPTN 082 trial with AGYW in this setting) and an alpha of 0.05, we will have 80% power to detect at least a 20% difference in the proportion with adherence between arms.

For our primary outcome of common mental disorder symptoms, if we assume 50% prevalence of symptoms of common mental disorders (again, as was seen in the HPTN 082 and PrEP SMART trials) and an alpha of 0.05, we will have 80% power to detect at least a 25% difference in the proportion with symptoms of common mental disorders between arms.

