Covariate(s) of interest: For the per protocol analysis, the regression model will adjust for potential confounding from covariate characteristics assessed at baseline and follow-up, which may include:

• Sociodemographic characteristics; sexual behaviors; gender-based violence (GBV); symptoms of common mental disorders; self-esteem; and level of engagement with the intervention.

Statistical analyses:

1) We will compute descriptive statistics to describe the full study population of randomized individuals at baseline and to describe retention over time in both arms of the intervention. We will also summarize reasons for discontinuing PrEP.

- 2) We will compute descriptive statistics for missing data, including the pattern of missingness across visits for both arms of the intervention, and factors associated with missingness. All information from participants with missing data will be examined to determine if any pattern is evident that would account for the missingness.
- 3) Primary analysis: We will conduct an intent-to-treat analysis using a Poisson regression with robust standard errors to assess the effect of the Youth Friendship Bench SA plus SOC intervention compared to SOC services alone on SRQ-20 scores (with reduced symptoms of common mental health disorders defined as SRQ-20 scores < 7) at 12 weeks after randomization. The main effect can be interpreted as the difference in symptoms of common mental health disorders at 12 weeks between the SA plus SOC arm and SOC only arm of the intervention. The effect of the intervention will be estimated as a relative risk (RR) from the Poisson regression model, with treatment arm assigned at first randomization as the only predictor.

Per-protocol analyses: We will also conduct a per-protocol analysis using the same procedures described above but restricting to participants who received full doses of the Youth Friendship Bench SA plus SOC intervention compared to SOC services alone as described above in the *Measures of intervention use* section. Adjustment for covariates of interest will be performed as described above.

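### The 80% power for the SRQ-20 co-primary does not hold for a two-sided 5% test after the plan's own 10-15% loss: about 71-74%, with sidedness and the dropout basis unstated

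*Protocol*

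**What the plan says.** Protocol section 11.3 and the SAP (Sample size; Power calculations) carry the same text. On numbers: "We will randomize 110 AGYW in a 1:1 ratio", and "we expect to retain 85-90% of AGYW through three months of follow-up". For the mental health co-primary the premise is "if we assume 50% prevalence of symptoms of common mental disorders", "and an alpha of 0.05", and the claim is "we will have 80% power to detect at least a 25% difference in the proportion with symptoms of common mental disorders between arms".

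The outcome is binary, an SRQ-20 score below 7 at Week 12 (Protocol 11.2.2). The SAP analyses it by robust Poisson regression "with treatment arm assigned at first randomization as the only predictor" (Co-Primary Analysis 2, Primary analysis). SAP Appendix Table 2 reports a relative risk with a 95% confidence interval and a p-value.

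Four things are not stated: whether the test is one- or two-sided, whether 110 is before or after loss, which arm the 50% belongs to, and whether the 25% is absolute or relative. The adherence sentence just before it does attach its 40% to the standard-of-care arm.

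**The concern.** Retention and power stand side by side in one section, but the power sentence does not say which number of women it uses. At the expected retention only about 47-50 of the 55 women per arm will have a Week 12 score. A two-sided comparison of 50% with 25% on that number falls short of 80%.

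This is one of two co-primary outcomes. If it shows no clear effect, readers will weigh that result against the printed 80%, so the figure should describe the analysis that will be done on the women expected to provide the outcome.

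**Working it through.** **Inputs.** 110 randomised 1:1, retention 85-90%, 50% prevalence, 25% difference, alpha 0.05 (Protocol 11.3). Assumptions: the 50% is the standard-of-care rate and the 25% is absolute, so p1 = 0.50, p2 = 0.25, d = 0.25. Recasting the outcome as SRQ-20 below 7 (50% versus 75%) leaves the normal-approximation results unchanged.

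**Formula.** With n per arm, power = Φ[(d√n − z·s0)/s1].
- s1 = √(0.50×0.50 + 0.25×0.75) = 0.6614.
- Pooled variance: s0 = √(2×0.375×0.625) = 0.6847. Unpooled variance: s0 = s1.
- z = 1.960 two-sided, 1.645 one-sided.

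**Step 1: the plan's own figure.** Two-sided, no loss, n = 55, so d√n = 1.854.
- Pooled: (1.854 − 1.342)/0.6614 = 0.774, power 78.1%.
- Unpooled: (1.854 − 1.296)/0.6614 = 0.843, power 80.0%.

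The unpooled formula reproduces 80% at exactly 110 women with no loss.

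**Step 2: a second route to the same figure.** One-sided 0.05, pooled, needs n = [(1.645×0.6847 + 0.842×0.6614)/0.25]² = 45.3, so 46 per arm. With 15% loss, 92/0.85 = 108.2, so 109 randomised. This also lands on the printed number, with loss included.

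**Step 3: apply the printed retention.** 110×0.90/2 = 49.5 per arm; 110×0.85/2 = 46.75 per arm. Two-sided, pooled:
- n = 49.5: (1.759 − 1.342)/0.6614 = 0.630, power 73.6%.
- n = 46.75: (1.709 − 1.342)/0.6614 = 0.556, power 71.1%.

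| Test | No loss (55) | 10% loss (49.5) | 15% loss (46.75) |
|---|---|---|---|
| Two-sided, pooled | 78.1% | 73.6% | 71.1% |
| Two-sided, unpooled | 80.0% | 75.8% | 73.4% |
| Two-sided, arcsine | 78.4% | 74.1% | 71.6% |
| One-sided 0.05, pooled | 86.4% | 83.1% | 81.1% |

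**Step 4: the test as written.** With arm as the only predictor, robust Poisson regression is in effect a Wald test of the log relative risk. Exact binomial enumeration for SRQ-20 below 7, 50% versus 75%, two-sided 0.05, gives 77.0% at 55 per arm, 73.9% at 50, 72.8% at 49 and 70.3% at 47. A continuity-corrected formula is lower still, 63-66% after loss; it is left out of the quoted range because the plan's test applies no such correction.

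**Step 5: detectable difference.** Solving the formula for d from 50% at 80% two-sided power gives, pooled, 25.5 points with no loss, 26.8 at 10% loss and 27.5 at 15% loss. Unpooled, the last two are 26.2 and 26.8.

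**Step 6: number needed, for scale only.** Pooled, two-sided: [(1.960×0.6847 + 0.842×0.6614)/0.25]² = 57.7, so 58 per arm and 116 with outcomes. That means 116/0.90 = 129 or 116/0.85 = 137 randomised. Unpooled needs 55 per arm, so 110/0.90 = 123 or 110/0.85 = 130.

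**The case against.** **Dropout may have been counted.** A reader might infer that the sponsor left dropout out of the calculation. The documents do not support that as a fact. Step 2 shows that a one-sided 0.05 test with 15% loss also arrives at about 110, and sidedness is never stated. Two points weigh against the one-sided route. The objectives are framed as comparisons and the table shells carry 95% intervals. A one-sided convention also does not rescue the adherence claim in the same section: 40% versus 60% has 68% one-sided power at 55 per arm and 62-64% after loss, against a stated 80%. These points make omission the likelier account without proving it. The table shells show how results will be reported, not which alpha went into the power sentence.

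**Part of the gap is the formula.** Against the printed 80%, 71-74% is a shortfall of 6-9 points. About 2 of those are the pooled-unpooled choice (80.0 − 78.1). Loss itself costs about 4-7 points (78.1 to 73.6-71.1 pooled; 80.0 to 75.8-73.4 unpooled). This stands.

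**Imputation.** The SAP plans multiple imputation of missing outcomes, so all randomised women may stay in the analysis. A reader might answer that this recovers nothing because arm is the only predictor, but that describes the analysis model. The imputation model may use other variables, and SRQ-20 is collected at enrolment and Week 4. The gain is probably small. If imputation recovered half of the lost information (an assumption), the effective n would be (55 + 46.75)/2 = 50.9 to (55 + 49.5)/2 = 52.25 per arm, and pooled power 75-76%. The 71-74% should therefore be labelled complete-case.

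**Inferred inputs.** 50% versus 25% is a reading of the text. It is the favourable one: a relative 25% reduction (50% versus 37.5%, d = 0.125) would give only about 23-24% pooled power after loss.

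**Conclusion.** The point holds as a mismatch between a stated figure and the analysis it describes. For 50% versus 25%, a two-sided 5% test on 47-50 women per arm has about 71-74% complete-case power by the pooled formula, and 70-76% across the pooled, unpooled, arcsine and exact calculations. It reaches 80% power for a difference of about 26-27.5 points. The printed 80% needs either a two-sided test with no loss or a one-sided test with loss.

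The conclusion rests on four assumptions: the test is two-sided, as the 95% intervals and p-values imply; the 25% is absolute; the 50% is the standard-of-care rate; and imputation recovers little. The arithmetic is firm. How the sponsor arrived at 80% cannot be settled from the documents. Nor do they show that the trial must be enlarged: the power statement is wrong for the implied analysis, but that does not make the design invalid.

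**What to change.** In Protocol 11.3 and in the SAP's Power calculations, state that the test is two-sided, that 110 is the number before loss, that the 50% refers to the standard-of-care arm, and that the difference is in percentage points. Then replace the SRQ-20 power sentence with wording such as:

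*With 110 randomised and 85-90% retained (47-50 per arm), a two-sided 0.05 test has about 71-74% power for 50% vs 25%, and 80% power for a difference of about 27 points. These are complete-case figures.*

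If a one-sided test was intended, say so and bring the SAP's reporting into line with it.

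The cost is a sentence or two in each document. Sample size, endpoint and analysis do not change; the stated power becomes somewhat less favourable.

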11.4. Data Analysis

11.4.2. Primary Analyses

We will use Poisson regression with robust standard errors to assess the effect of standard-ofcare services compared with our adapted mental health intervention on TFV levels measured in urine (with adherence defined as TFV \geq 1500 ng/mL) at 12 weeks after randomization. We will also use Poisson regression with robust standard errors to assess the effect of standard-of-care services compared with our adapted mental health intervention on symptoms of common mental disorders at 12 weeks after randomization, using an SRQ-20 score of 7 as our threshold.

11.4.3. Secondary Analyses

We will use Poisson regression with robust standard errors to assess the effect of standard-ofcare services compared with our adapted mental health intervention on TFV levels measured in urine (with adherence defined as TFV \geq 1500 ng/mL) at 4 weeks after randomization.

The correlates of response (PrEP adherence based on TFV levels, symptoms of common mental disorders based on the SRQ-20) at 12 weeks will be assessed using logistic regression modelling, evaluating the covariates described in the endpoints section above.

Survival analysis will be used assess the effect of the adherence strategies as well as individual characteristics (demographics, etc.) on time to PrEP discontinuation for those who choose to stop PrEP before 12 months.

We will analyze qualitative data (in-depth interviews, clinic observation field notes) using an inductive and deductive coding approach and will use descriptive statistics to summarize quantitative data on intervention acceptability, feasibility, and appropriateness and SAEs and AESIs.

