	All participants will be offered PrEP in accordance with national PrEP guidelines as part of routine care. We will also provide all participants with brief PrEP adherence counseling based on their urine POC assay results at the Week 4 and Week 12 visits. This adherence counseling will be in addition to their Youth Friendship Bench SA or standard-of-care mental health service delivery	
	All participants will be followed for three months.	
	We will conduct qualitative data collection with a purposive sample of up to 30 AGYW in the trial (between Week 4 and Week 12) and 15 health care providers and key informants to characterize themes around acceptability, appropriateness, and feasibility of Youth Friendship Bench SA and the urine POC TFV assay. We will also conduct ethnographic clinic observations throughout the study period (to 2 times per month).	
Study Population:	HIV-uninfected women ages 18-25 in Johannesburg, South Africa, who have symptoms of common mental disorders as evidenced by a score greater than or equal to 7 on the SRQ-20.	
Study Size:	Up to 110 women who accept PrEP will be consented and randomized	
Outcome measures	We have co-primary outcomes: PrEP adherence and common mental disorder symptoms. The PrEP adherence primary outcome is the proportion with PrEP adherence at Month 3, defined as tenofovir (TFV) concentrations ≥1500 ng/mL in urine measured using a urine POC assay. We will also assess the short-term effect of the Youth Friendship Bench SA intervention on PrEP adherence using the urine POC assay at the Week 4 visit.	
	The mental health related primary outcome is the proportion with reduced symptoms of common mental disorders (SRQ-20 scores <7) at Month 3, measured using the SRQ-20.	
Study Duration:	Approximately 36 months, including submissions to Institutional Review Boards (IRBs) and study start up activities (6 months), recruitment and enrollment (12 months), participant follow up (3 months following the last enrolled participant), and data analysis (remaining time through 36 months).	
Study Site:	Ward 21 public clinic in Johannesburg, South Africa.	

OVERVIEW OF STUDY DESIGN

Figure 1. Study schema for the evaluation of the Youth Friendship Bench SA counseling intervention

AGYW=adolescent girls and young women; SRQ-20=self reporting questionnaire 20-item; SOC=standard of care; IDIs=indepth interviews; POC=point-of-care

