7.0 STUDY DESIGN

7.1. Design

This is a single-site effectiveness-implementation randomized controlled trial. 110 participants are planned and will be consented to have 12 weeks of follow-up. All participants will be offered PrEP by clinic personnel as part of standard PrEP prescribing practices, and PrEP delivery (including PrEP readiness assessment, HIV testing, PrEP adherence counseling that is not part of the urine point-of-care drug-level feedback, and PrEP prescribing) is not considered a research procedure.

Each participant will be randomized in a 1:1 ratio to receive either standard-of-care plus our Youth Friendship Bench SA mental health intervention package or standard-of-care alone. Our coprimary endpoints are PrEP adherence assessed using tenofovir detected in a urine POC assay performed at the Week 12 study visit and symptoms of common mental disorders assessed using the SRQ-20 at the Week 12 visit. All participants will also receive PrEP adherence counseling based on results of their urine POC TFV assay at the Week 4 and 12 visits ("drug-level feedback counseling"), in addition to their standard-of-care or Youth Friendship Bench SA services.

Standard-of-care mental health services: As specified in the Adult Primary Care Guidelines,¹⁰⁸ standard-of-care services include a 2-item symptom assessment at enrollment and a brief screen about whether their mental health symptoms have changed at Week 4 and Week 12, to align with PrEP refill schedule. Symptom assessment is to be followed by escalation and referral for mental health care assessment by a trained health care professional (e.g. social worker, psychologist, or medical doctor) as needed. The initial symptom assessment includes two questions asking if one has felt down, depressed, or hopeless or has little interest or pleasure in doing things (**Appendix 1**). This assessment is administered by a counselor or nurse, or could be self-administered. The Adult Primary Care Guidelines specify that clients who screen positive on these initial questions are then asked about

somatic symptoms (if the client has five or more somatic symptoms and these symptoms impair their ability to engage in daily tasks, it is likely that they have a common mental disorder and will need further referral and care). The social worker may then refer the client for acute hospitalization, psychotherapy, or pharmacotherapy as needed.

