8.3.2. Screening and Enrollment Visit

The screening and enrollment visit may be conducted as a split visit as needed. Young women who are eligible and agree to study participation will be consented for 3 months of follow-up. The following procedures will take place:

- 1. Review and obtain written informed consent.
- 2. Confirm/Record locator information and phone number and contact preferences.
- 3. Assign a unique study identification number
- Assess eligibility (e.g., age 18-25 years, newly initiating PrEP at the clinic, symptoms of common mental disorders), including Adult Primary Care Guidelines screening questions and the SRQ-20
 - a. If participants report suicidal ideation or intent, have untreated or severe somatic symptoms or have other active psychiatric symptoms (e.g., hallucinations) the participant will be referred for assessment by a trained health professional (see Section 4.2).

Participants that are already on treatment with stable symptoms may continue to randomization.

- 5. Offer enrolment to eligible participants and refer ineligible for additional services if needed.
- Collect additional data on past mental history, participation in other mental health or HIV interventions, and other psychosocial and behavioral data (see Section 6).
- 7. Randomize participant to either Youth Friendship Bench SA intervention or the standard-of-care condition.
 - a. Participants randomized to the Youth Friendship Bench SA intervention will complete their first counseling session at this visit.
 - i. Collect preferences for SMS appointment reminders (see Section 4.3)
 - ii. Schedule participant for their Week 2 visit in 14 days. They will be offered the option to complete the Week 2 visit in-person or remotely (over the phone).
 - Standard-of-care participants will be scheduled for their next clinic visit at Week 4 in 30 days. They will not receive appointment reminders or remote services.

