8.3.4. Week 4 Visit

- 1. Confirm consent
- 2. Confirm locator information and update as needed
- 3. Collect psychosocial and behavioral data additional data (see Section 6).
- 4. Assess symptoms of common mental disorders
 - a. All participants will receive assessments per APC guidelines and referrals as needed. They will also complete the SRQ-20 with the lay counselor.
 - b. Participants Youth Friendship Bench SA arm will complete their 3rd counseling session.
- 5. Schedule participant's next visit
 - a. Standard-of-care participants will be scheduled for their Week 12 visit in 60 days.
 - b. Youth Friendship Bench SA participants will be scheduled for their Week 8 visit in 30 days. They will be offered the option to complete the Week 8 visit in-person or remotely (over the phone).
- 6. All participants will be asked to provide a urine sample for the tenofovir (TFV) point-of-care (POC) assay. Urine POC assay testing and drug-level feedback counseling based on assay results will be conducted by the lay Youth Friendship Bench SA for participants in both arms and proceed as described in Section 5.1.2. The urine assay results will be used for research purposes only and will not be included in the clinic record.
- 7. Schedule in-depth interviews for AGYW between the Week 4 and Week 12 study visit.

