10.0 DATA COLLECTION

10.1. Quantitative data collection

Demographic and behavioral data will be collected, including information on symptoms of common mental disorders, drug and alcohol use, GBV, post-traumatic stress symptoms, coping behavior, self-esteem, sexual relationship power, and sexual behavior (e.g., number of partners, vaginal sex with partners).

We will access the participant's clinic record to obtain information on age, HIV status, and PrEP status at screening. We will also abstract information on PrEP refills (bottle dispensed, dates of dispensation, and PrEP terminations) from the clinic records during the participant's three-month follow-up period.

Symptoms of common mental disorders will be assessed using the SRQ-20, which will be interviewer-administered by the lay counselors at enrollment, Week 4, and Week 12. Data on depressive symptoms (using the Patient Health Questionnaire-9 [PHQ-9]), anxiety (the Generalized Anxiety Disorder questionnaire [GAD-7]), history of mental health conditions and

services received, drug and alcohol use, GBV, and post-traumatic stress symptoms will also be interviewer-administered on study Case Report Forms (CRFs). All other demographic and behavioral data will be self-collected by participants using a tablet application. Research staff will be available in the clinic to provide guidance and assistance in completing the questionnaire as needed. De-identified data will be collected using REDCap and stored on a secure server.

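### The protocol's survival analysis of PrEP discontinuation names a 12-month horizon in a trial with 12 weeks of follow-up and, read literally, includes only women who stop, so it could not estimate the arm effect on stopping

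*Protocol*

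**What the plan says.** Protocol 11.4.3 (Secondary Analyses) gives one sentence to this analysis. Its purpose is to assess the effect of the adherence strategies and of individual characteristics on "time to PrEP discontinuation for those who choose to stop PrEP before 12 months". The sentence gives no time origin, event definition, censoring rule or model. The term for the strategies does not name either arm of this mental-health trial.

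Other sections fix the period of observation:

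- Protocol 7.1: "110 participants are planned and will be consented to have 12 weeks of follow-up". The protocol Schema says: "All participants will be followed for three months".
- Protocol 8.3.6: participants are exited at the Week 12 visit.
- Protocol 10.1: stopping dates can come from refill and termination records, which are abstracted for a limited window: "PrEP terminations) from the clinic records during the participant's three-month follow-up period".

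Section 11.2 does not list time to discontinuation among the primary, secondary or exploratory endpoints. The SAP, last updated in July 2024, has no survival analysis. On this topic it only undertakes to summarize reasons for stopping PrEP, under both co-primary analyses and Secondary Analysis 1.

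**The concern.** There are two separate problems, and correcting one leaves the other.

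The first is the horizon. A 12-month window cannot be filled from 12 weeks of follow-up and three months of clinic records.

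The second is the analysis set. A survival comparison between arms needs the women who do not stop, because they carry the information that the risk is lower in one arm. If only stoppers are analysed, every woman has the event and nobody is censored. The set has then been selected on something that happens after randomization, so the comparison is no longer one of randomized groups. Replacing months with weeks does not cure this.

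At stake is a secondary answer on PrEP persistence. The background (protocol 5.1) describes steep falls in adherence and persistence 1-3 months after initiation, which is the window this trial observes.

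**Working it through.** **Step 1: the horizon.** The plan states no event count or power for this analysis; its only figure is 12 months. The visit schedule does not reproduce it.

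- Standard-of-care arm: "Standard-of-care participants will be scheduled for their next clinic visit at Week 4 in 30 days" (8.3.2), then "Standard-of-care participants will be scheduled for their Week 12 visit in 60 days" (8.3.4). Total 30 + 60 = 90 days.
- Intervention arm (8.3.2 to 8.3.5): 14 + 14 + 30 + 30 = 88 days.
- Share of 12 months: 90/365 = 0.247 and 88/365 = 0.241.

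Scheduled observation therefore covers about a quarter of the stated window, and no stop after about month 3 can be seen. The only 12-month period the protocol gives for this trial is enrollment (Schema and 11.3).

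**Step 2: the effect of keeping only stoppers.** Inputs from the documents: 110 women randomized 1:1 (11.3), so 55 per arm, and 90 days of observation. Assumed, because the documents give no discontinuation rates: the proportions stopping by day 90, exponential stopping times and no loss to follow-up.

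Formulas, with p the proportion stopping by day 90:

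- Hazard: λ = −ln(1 − p)/90.
- True hazard ratio (HR), intervention to standard of care: ln(1 − p_int)/ln(1 − p_soc).
- Mean time to stopping among stoppers: 1/λ − 90(1 − p)/p.

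For 60% (standard of care) versus 40% (intervention):

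- HR = ln(0.6)/ln(0.4) = 0.511/0.916 = 0.56.
- Standard of care: λ = 0.916/90 = 0.01018; mean = 98.2 − 90 × 0.4/0.6 = 98.2 − 60 = 38.2 days.
- Intervention: λ = 0.511/90 = 0.00568; mean = 176.2 − 90 × 0.6/0.4 = 176.2 − 135 = 41.2 days.

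Nearly halving the hazard thus moves the mean among stoppers by three days.

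Simulation: two-sided 0.05 log-rank test, 1,500 runs per scenario, with the Cox HR taken as the median of 200 runs.

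| Stopping by day 90, SOC vs intervention (assumed) | True HR | Mean days among stoppers | Stoppers only: HR, rejection rate | All randomized: HR, rejection rate |
|---|---|---|---|---|
| 60% vs 60% | 1.00 | 38.2 vs 38.2 | 0.97, 5.2% | 0.99, 5.0% |
| 60% vs 40% | 0.56 | 38.2 vs 41.2 | 0.91, 6.3% | 0.55, 58% |
| 50% vs 30% | 0.51 | 39.8 vs 42.3 | 0.96, 6.6% | 0.49, 57% |
| 40% vs 20% | 0.44 | 41.2 vs 43.3 | 0.96, 6.5% | 0.44, 65% |
| 70% vs 40% | 0.42 | 36.2 vs 41.2 | 0.82, 10.5% | 0.42, 93% |

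Check of the second row by the Schoenfeld formula: expected events = 55 × 0.6 + 55 × 0.4 = 55; |ln 0.557| × √(55/4) − 1.96 = 0.585 × 3.708 − 1.96 = 0.21; power Φ(0.21) = 58%, which agrees.

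**Step 3: whether other text settles the analysis set.** It does not. Section 11.2 has no such endpoint, the SAP has no such analysis, and no passage says that women still on PrEP are kept and censored.

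**The case against.** The strongest reply is that the sentence is carelessly worded but the intention is sound. Survival methods exist to handle people without the event, so the clause about women who choose to stop may describe the event and not the analysis set. Every other endpoint and quantitative analysis in section 11 is set at 4 or 12 weeks, so months is probably a slip for weeks. The SAP does not carry the analysis forward and may have let it lapse.

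Much of this stands. If weeks was meant, nothing is unobserved. A reader might infer that three quarters of the outcome data will be missing, but that takes a likely slip at face value. A reader might also infer that the protocol deliberately drops continuers; the text allows that reading but does not establish it.

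Two further inferences fail even on the literal reading. The analysis would not be empty, because women who stop within 12 weeks are recorded. Nor is it incapable of showing any difference between arms, since timing among stoppers can differ. What it cannot estimate is the arm effect on stopping.

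It would also go too far to say that the analysis bears on the trial's central problem. The background pairs persistence with adherence, and adherence has its own co-primary endpoint.

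The reply does not remove the need for a correction. An analyst has no text that resolves the analysis set, event or censoring, and the SAP does not say that the analysis was withdrawn.

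**Conclusion.** The point holds as a defect of wording and specification in a secondary analysis. The 12-month horizon contradicts the 12-week follow-up and the three-month record window; this rests on the text alone. Read literally, the analysis also conditions on stopping and cannot estimate the arm effect on the risk of stopping.

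In the four scenarios with a true effect (HR 0.42 to 0.56), the stoppers-only HR was 0.82 to 0.96 with 6% to 10.5% power, against 57% to 93% power in all randomized women. These sizes depend on assumed stopping proportions, exponential times and complete follow-up. The loss of the signal follows from the selection; the exact figures do not come from the documents.

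The practical weight is small: neither co-primary analysis depends on this one, and the SAP does not include it.

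**What to change.** Either restate the analysis or delete the sentence from protocol 11.4.3. If it is kept:

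- **Estimate:** time from randomization to clinic-recorded PrEP discontinuation through Week 12, in all randomized women by assigned arm, with Kaplan-Meier curves and a Cox model. Randomization is the natural origin because protocol 8.1 allows recruitment at PrEP initiation or at follow-up.
- **Censoring:** women still on PrEP at Week 12; women lost to follow-up at last contact or last clinic record. Section 11.3 expects 85-90% retention, so the second rule will be used.
- **Event and date:** define both from the refill and termination records, and say whether and when a missed refill counts as stopping. Without that rule, a woman who simply ceases to attend could be censored when she has in fact stopped.
- **Listing:** name the arms in place of the adherence strategies, and enter the analysis in 11.2.3 and the SAP.

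The cost is wording in the protocol and SAP. Refill and termination data are already planned for abstraction (10.1), and women who do not adhere to PrEP stay in follow-up (8.3.8), so no new data are needed.
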